- Bethesda assay: We will measure the presence of inhibitors using the Bethesda assay with Nijmegen modification. A titre of at least 0.6 Bethesda Units is required to be positive for this assay. The cut-off point for low-titre vs high-titre inhibitors is 5.0 Bethesda Units. [92]
- Low-titre inhibitor assay: To assess the presence of low-titre inhibitors, we will use a lowtitre inhibitor assay. ([name], personal communication)
- ELISA: We will assess the presence and characteristics of FVIII-specific antibodies in our full cohort using a highly sensitive and fully validated ELISA platform developed by Whelan et al.
 [70] In patients who are positive for antibodies using this assay we will characterize the isotype (IgA, IgM and IgG) and for the IgG isotype also the subclass (IgG1 to 4). Samples with confirmed specificity for FVIII will also be assessed for apparent affinity.

The apparent affinities of FVIII-specific antibodies for all immunoglobulin isotypes and IgG subclasses will be assessed using a competition-based ELISA approach by Hofbauer et al. The affinity assessment is based on the availability of antibody for binding to FVIII-coated ELISA plates after competition with FVIII in solution. [71]

• Other laboratory tests such as:

- FVIII and FIX activity using one-stage assay
- FVIII and FIX activity using chromogenic assay
- FVIII and FIX antigen level
- FVIII genotype (if unknown)
- FVIII haplotype
- HLA/IL-10/TNFα/CTLA4/HO-1/FcgR gene variants

Second visit (50 adult participants):

Based on the results of the first analyses, we will draw an additional 50 mL of blood in 50 selected participants during a second visit to the haemophilia treatment centre. This second sample will be only be used for this substudy and will not be stored in the biobank. Blood samples will be used for the following experiments: • **Regulatory T cell count:** Regulatory T cell count will be assessed using both flow cytometry and a quantitative real-time PCR assay developed by Epiontis (Epiontis Treg assay).

Flow cytometry

After stimulation of PBMCs with FVIII, we will quantify all T-cell subsets using flow cytometry. PBMCs will be stained with monoclonal antibodies against cell receptors specific for a certain T-cell subset (e.g. CD4+, CD25high, CD127low, FOXP3+ for T-regulatory cells) [93] and markers of T-cell activation (e.g. CD154) [94].

Epiontis Treg assay

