Determinants: The following parameters of the CAT assay will be used as determinants; lag-time, time to peak, peak height and endogenous thrombin potential. FVIII concentration (measured using the chromogenic assay) will also be used as a determinant.

Endpoint: The modified bleeding severity score developed by Schulman et al [97] will be applied to this study population (see paragraph 5.1.3) and used as a dichotomous outcome. Mild bleeders will be defined as being in the lowest two quartiles of the modified bleeding severity score, severe bleeders will be defined as being in the highest two quartiles of the modified bleeding severity score. **Statistical analysis:** The CAT assay parameters and FVIII concentration will be used to predict if a patient is a mild or a severe bleeder (based on the modified bleeding severity score). We will quantify diagnostic performance by constructing ROC-curves for each parameter of the CAT assay

and for FVIII concentration. We will then test if the AUROC of each parameter of the CAT assay differs significantly from the AUROC of the chromogenic assay. This analysis will be performed for the total population and separately for each category of severity.

6.4.2 To assess the usefulness of the Nijmegen Haemostasis Assay (NHA) in relation to clinical phenotype:

Primary objective 1: To assess the association between the results of the NHA and the self-reported clinical bleeding phenotype of patients with severe, moderate and mild haemophilia A and B.
Study design and population: A cross-sectional study design will be used. The population will consist of all haemophilia A and B patients in the Netherlands.

Determinant: The following parameters of the NHA will be used as determinants; lag-time, thrombin peak-time, thrombin peak-height, area under the curve (AUC), fibrin lysis time (FLT), plasmin peak-height and plasmin potential.

Potential confounders: FVIII/FIX genotype, VWF antigen levels and VWF activity.

Endpoint: The modified bleeding severity score developed by Schulman et al [97] will be used as the endpoint (see paragraph 5.1.3). **Statistical analysis:** The association between each parameter of the NHA and bleeding severity will be assessed using linear regression.

Primary objective 2: To evaluate if the NHA can accurately diagnose the self-reported clinical bleeding phenotype of patients with severe, moderate and mild haemophilia.

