Study design and population: A cross-sectional study design will be used. The population will consist of all haemophilia A and B patients in the Netherlands.

Determinants: The following parameters of the NHA will be used as determinants; lag-time, thrombin peak-time, thrombin peak-height, area under the curve (AUC), fibrin lysis time (FLT), plasmin peak-height and plasmin potential. FVIII concentration (measured using the chromogenic assay) will also be used as a determinant.

Other potential predictors of clinical bleeding phenotype: FVIII/FIX genotype, VWF antigen levels and VWF activity.

Endpoint: The modified bleeding severity score developed by Schulman et al [97] will be applied to this study population (see paragraph 5.1.3) and used as a dichotomous outcome. Mild bleeders will be defined as being in the lowest two quartiles of the modified bleeding severity score, severe bleeders will be defined as being in the highest two quartiles of the modified bleeding severity score. **Statistical analysis:** Firstly, we will perform univariate logistic regression using FVIII concentration as

the determinant (the basic prediction model). To quantify the incremental value of the NHA parameters, they will be added to the basic prediction model to create the full prediction model. For internal validation, bootstrapping techniques will be used to reduce overfitting. Agreement between observed and predicted outcomes will be assessed using a calibration plot. Discrimination will be assessed by calculating the AUROC of the full model. The added value of the NHA will be assessed by comparing the AUROC of the basic model (only FVIII concentration) with the AUROC of the full model (FVIII concentration + NHA parameters).

6.4.3 To assess misclassification of disease severity by the one-stage clotting assay in haemophilia B patients:

Primary objective 1: To assess the extent of discrepancy in FIX activity level as measured by the one stage clotting assay to the chromogenic assay in patients with mild and moderate haemophilia B.
Study design and population: A cross-sectional study design will be used. The population will consist of all persons with mild and moderate haemophilia B.

Determinant: FVIII activity level, as determined by the chromogenic assay.

Endpoint: FVIII activity level, as defined using the one-stage clotting assay.

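### The NHA added-value analysis (6.4.2, objective 2) covers haemophilia A and B but compares only against FVIII, which is not the deficient factor in haemophilia B

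*Protocol*

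**What the plan says.** Protocol section 6.4.2, primary objective 2, sets the population: "The population will consist of all haemophilia A and B patients in the Netherlands". The outcome is dichotomous and splits the cohort at its median: "Mild bleeders will be defined as being in the lowest two quartiles of the modified bleeding severity score", with the upper two quartiles as severe bleeders.

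On the comparator, "FVIII concentration (measured using the chromogenic assay) will also be used as a determinant". For the basic model, "we will perform univariate logistic regression using FVIII concentration as" the sole determinant. The NHA parameters are then added to give the full model, and added value is assessed by "comparing the AUROC of the basic model (only FVIII concentration) with the AUROC of the full model (FVIII concentration + NHA parameters".

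The objective also names "Other potential predictors of clinical bleeding phenotype: FVIII/FIX genotype, VWF antigen levels and VWF activity". FIX activity is not in that list and not in the basic model.

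Two other places bear on this. Section 4.1 defines severity by FVIII or FIX level. Section 5.1.2 lists "FVIII and FIX activity using chromogenic assay" among the tests on the first-visit sample.

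Section 6.4.1, secondary objective 2, tests the AUROC of each Calibrated Automated Thrombogram (CAT) parameter against that of chromogenic FVIII. Its 75 patients are 25 per severity class, and haemophilia type is not stated.

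**The concern.** The added-value question is whether the NHA tells us more than the factor assay already in use. That requires a comparator that measures each patient's own defect. FVIII does so in haemophilia A. In haemophilia B it is unrelated to severity and is not expected to be low, so a severe B patient is placed among the least affected. The NHA is studied as a global measure of haemostasis and should respond to either deficiency. Part of any AUROC gain over FVIII alone may therefore be information that a FIX assay would have supplied.

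Section 1.4 says that these assays, if they prove useful, could help to tailor treatment individually. A gain produced by the wrong comparator would be a poor basis for that conclusion.

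**Working it through.** **The plan's own figure.** Section 4.4: 1800 × 0.70 = 1260 expected participants, which reproduces. The protocol gives no AUROC, haemophilia B share or power for this comparison, so everything below on size rests on stated assumptions.

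**Does any text supply FIX?** No passage restricts objective 2 to haemophilia A, stratifies it by type or substitutes FIX in haemophilia B. Genotype could reveal type, but it is only a potential predictor. The basic model is univariate, and the full model adds only NHA parameters.

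**Step 1: effect on the comparator, by hand.** Let b be the B share, equal in both bleeder classes, and A the AUROC of the correct deficient factor. Assume that every B patient has higher FVIII than every A patient and that FVIII is uninformative within B. Take one severe and one mild bleeder:

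- both A, probability (1−b)²: ranked correctly with probability A
- both B, probability b²: 0.5
- severe bleeder A, mild bleeder B, probability b(1−b): always correct
- severe bleeder B, mild bleeder A, probability b(1−b): always wrong

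AUROC = (1−b)²A + 0.5b² + b(1−b). With an assumed A = 0.80:

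- b = 0.10: 0.648 + 0.005 + 0.090 = 0.743
- b = 0.15: 0.578 + 0.011 + 0.128 = 0.717
- b = 0.20: 0.512 + 0.020 + 0.160 = 0.692

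The comparator loses 0.057, 0.083 and 0.108. This is the drop in the basic model, not the inflation of the NHA gain.

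**Step 2: effect on the gain, by simulation.** N = 1260, 150 replicates per scenario. Assumptions, not in the protocol except for the class limits of section 4.1:

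- severity mix 40/15/45% (severe/moderate/mild)
- deficient factor log-uniform within 0.001–0.01, 0.01–0.05 and 0.05–0.40 IU/ml
- FVIII in haemophilia B uniform 0.5–1.5 IU/ml, unrelated to bleeding
- bleeding score = −L + standard normal noise, where L is the standardised log deficient factor, split at the median
- NHA = L + noise with SD 0.5 (good proxy, AUROC alone about 0.83) or SD 1.0 (noisier, about 0.76)

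The simulated NHA carries nothing beyond the deficient factor, so its true added value is zero.

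Log-scale factor level, FVIII-only comparator:

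| B share | Basic AUROC | Gain, good proxy | Gain, noisier proxy |
|---|---|---|---|
| 0% | 0.86 | 0.000 | 0.000 |
| 5% | 0.83 | +0.017 | +0.002 |
| 10% | 0.79 | +0.046 | +0.019 |
| 15% | 0.76 | +0.075 | +0.041 |
| 20% | 0.73 | +0.104 | +0.065 |

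With the deficient factor as comparator (FVIII in A, FIX in B), the basic AUROC is 0.86 and the gain 0.000 at every share.

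Untransformed factor level entered linearly:

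- Good proxy: gain +0.038, +0.068 and +0.102 at 10, 15 and 20%, against about −0.013 with the correct factor.
- Noisier proxy: −0.052, −0.025, +0.005 and +0.035 at 5, 10, 15 and 20%, against about −0.017 with the correct factor. At 5% and 10% the gain is not inflated.

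**Step 3: CAT, only if haemophilia B is included.** The comparison is head to head. With n = 75, equal severity classes, the good proxy and 1500 replicates, a true difference of −0.03 became +0.03, +0.06 and +0.09 at B shares of 10, 15 and 20%. With no B patients it stayed at −0.03.

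**The case against.** The strongest reply is that FVIII is a drafting slip for the relevant factor. Section 6.4.3 supports this. It concerns haemophilia B only and its objective names FIX, yet its determinant, endpoint and discrepancy ratio are written as FVIII. Severity is defined by either factor and chromogenic FIX will be measured, so an analyst might well use FIX in haemophilia B. This stands as an account of intent, and a reader should not infer that the authors chose a comparator meant to fail. It does not remove the point: the protocol fixes the model and the metric, and following the text gives the wrong analysis.

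Three other readings go further than the protocol allows.

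- **That CAT has the same defect.** Section 6.4.1 has no basic or full model, and nothing says that its 75 patients include haemophilia B. The spiking of FIX-deficient plasma is an in vitro experiment under a different objective. It suggests inclusion but does not establish it. If all 75 have haemophilia A, the issue does not arise there.
- **That a loss of 0.06 to 0.11 is the bias in favour of the NHA.** It is the fall in the comparator's AUROC under assumed inputs.
- **That the gain is always inflated.** It was not with untransformed FVIII, a very noisy assay and a 5–10% share.

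It is also fair that added value is one part of this objective, beside calibration and the full model's own discrimination. Those do not escape entirely, because the full model carries FVIII too. With the good proxy on the log scale its AUROC was 0.834 to 0.838 at shares of 10–20%, against 0.860 to 0.862 with the deficient factor.

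**Conclusion.** Wrong as written, for the NHA analysis in section 6.4.2, primary objective 2. The population includes haemophilia B, and the only factor level in the comparison is FVIII. The basic AUROC was lowered in every simulated scenario that contained haemophilia B.

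An inflated NHA gain is likely but not certain. With log-scale factor level and an assumed haemophilia B share of 10–20%, an assay of no true added value appeared to gain about 0.02 to 0.10. The size depends on that share, on how well the NHA tracks the deficient factor and on the scale of FVIII in the model. The protocol fixes none of these. For CAT, the only supported point is that haemophilia type needs to be stated.

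**What to change.** In section 6.4.2, primary objective 2, replace FVIII concentration with chromogenic activity of the deficient factor (FVIII in haemophilia A, FIX in haemophilia B), in the determinants and in both the basic and the full model. Report the NHA comparison by haemophilia type as well as pooled.

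In section 6.4.1, secondary objective 2, state whether the 75 patients include haemophilia B. If they do, use the deficient factor's activity as the comparator for the AUROC tests there too.

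The cost is protocol wording and a small amount of extra reporting. Section 5.1.2 already plans chromogenic FIX, so no further sample or assay is needed. The reported added value may turn out smaller, and the estimate within haemophilia B will be less precise than the pooled one.

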1.4.2 The Nijmegen Haemostasis Assay (NHA)

Although thrombin generation reflects the patients' coagulation status, it does not entirely represent the in vivo situation of the patient because it does not take fibrinolysis into account. The NHA uses two fluorescent substrates with non-interfering fluorescent excitation and emission spectra to measure both thrombin and plasmin generation in a single well by a fluorimeter. [60] The assay has been shown to be sensitive for severe haemophilia A, reflected by severely diminished thrombin generation and, due to lack of TAFI activation, increased plasmin generation. Moreover, the assay is also sensitive for FV Leiden, the poly A prothrombin mutation and variations in Protein C and S activity. [60, 61]

1.4.3 Misclassification of disease severity by the one-stage clotting assay in haemophilia B patients

FVIII and FIX activity is most often assessed using the one-stage clotting assay. [62] Several studies have observed a discrepancy in factor VIII activity between the one-stage clotting assay and the chromogenic assay in patients with mild and moderate haemophilia A. More specifically, a higher factor VIII activity was found with the one-stage assay, compared to the chromogenic assay. [63-67] Several studies have found that certain FVIII mutations are associated with this discrepancy. [64, 67, 68]

Misclassification of disease severity by the use of the one-stage clotting assay could have important ramifications; patients could be designated as having a milder bleeding risk, potentially leading to undertreatment of patients. All almost studies have focused on haemophilia A, with the exception of one recent conference paper [69] which also found a discrepancy between the one-stage clotting

assay and the chromogenic assay.

Given the scarcity of evidence for this phenomenon in the haemophilia B population, the HIN-6 study will assess the extent of misclassification of disease severity by re-evaluating the baseline FIX activity using the chromogenic FIX assay in all haemophilia B patients.

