Statistical analysis: This objective will firstly be explored using descriptive statistics. Furthermore, using the chromogenic assay as the reference test, we will calculate sensitivity and specificity (with corresponding 95%Cl's) for the one-stage clotting assay.

Primary objective 2: To evaluate the association between F9 genotype and discrepancy between the FIX activity levels as measured by the one-stage clotting assay and the chromogenic assay in patients with mild and moderate haemophilia B.

Study design and population: A cross-sectional study design will be used. The population will consist of all persons with mild and moderate haemophilia B.

Determinant: F8 and F9 genotype are the determinants. Information on F8/F9 genotype will be obtained from each patient's medical record.

Endpoint: A large discrepancy between the result of the one-stage clotting assay (FVIII: C_{1st}) and the result of the chromogenic assay (FVIII: C_{chr}) will be used as the endpoint. A large discrepancy between the result of the one-stage clotting assay and the chromogenic assay is defined as having a ratio of FVIII: C_{chr} to FVIII: C_{1st} lower than 0.6.

Statistical analysis: The association between F8/F9 genotype and a discrepancy between the results of the one-stage clotting assay and the chromogenic assay will be assessed using logistic regression.

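### Section 6.4.3 sets out to study FIX assay discrepancy in haemophilia B but defines its determinant, endpoint and discrepancy ratio on FVIII; its population also needs reconciling with section 1.4.3

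*Protocol*

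**What the plan says.** Section 6.4.3 of the protocol is headed as a study of severity misclassification by the one-stage assay in haemophilia B. Its first primary objective is "To assess the extent of discrepancy in FIX activity level as measured by the one stage clotting assay to the chromogenic assay", in mild and moderate disease. The second relates F9 genotype to the same FIX discrepancy. The objectives in section 2.4.3 agree.

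The operational lines under those objectives read differently:

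- Objective 1: "Determinant: FVIII activity level, as determined by the chromogenic assay".
- Objective 1: "Endpoint: FVIII activity level, as defined using the one-stage clotting assay".
- Objective 2: a large discrepancy is a "ratio of FVIII: C_{chr} to FVIII: C_{1st} lower than 0.6".
- Objective 2: "Determinant: F8 and F9 genotype are the determinants". The analysis line repeats F8/F9.

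For accuracy, the plan is that "using the chromogenic assay as the reference test, we will calculate sensitivity and specificity" for the one-stage assay. No target class or cut-off is named.

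On population, 6.4.3 states: "The population will consist of all persons with mild and moderate haemophilia B". The rationale in section 1.4.3 instead announces "re-evaluating the baseline FIX activity using the chromogenic FIX assay in all haemophilia B patients". Section 4.1 sets the class limits (severe below 0.01, moderate 0.01–0.05, mild above 0.05 up to 0.40 IU/ml) without saying which assay assigns the class.

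**The concern.** The factor at issue in haemophilia B is FIX and the gene is F9; the section's own objectives say so. A determinant, an endpoint and a discrepancy ratio built on FVIII:C answer a different question. The FVIII wording runs through both primary objectives, in lines that an analyst would program from. Followed as written, objective 1 would compare two FVIII assays in people with haemophilia B, and objective 2 would regress a FVIII discrepancy on genotype. Neither would say anything about the misclassification that section 1.4.3 sets out to study.

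A second, smaller matter is who enters the analysis. If severity was assigned by the same one-stage result that is being evaluated, leaving out the severe class selects patients on the test under study. Errors across the 0.01 IU/ml limit are then partly cut away, and accuracy for severe disease is settled by the selection.

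**Working it through.** **Plan's own figures.** Section 6.4.3 gives no sample size, power or expected rate. The only size statement is for the whole study (section 4.4): 1800 × 0.70 = 1260, which reproduces but plays no part here.

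**1. Objective against definition**

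| Item in 6.4.3 | Objective names | Definition uses |
|---|---|---|
| Objective 1, determinant | FIX | FVIII, chromogenic |
| Objective 1, endpoint | FIX | FVIII, one-stage |
| Objective 2, discrepancy ratio | FIX | FVIII:C chromogenic / one-stage, below 0.6 |
| Objective 2, genotype | F9 | F8 and F9 |

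The first three rows are contradictions. In the fourth, F9 is kept and F8 is an addition that the objective does not mention.

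**2. What a FVIII ratio can show.** No assay precision or bias is given in the protocol, so the following are assumptions: independent log-normal errors with SD s on each assay (0.15 or 0.25); mean one-stage/chromogenic FIX ratio b (1.0, 1.3 or 1.67); FVIII about 1 IU/ml in haemophilia B with no assay bias.

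The log of the chromogenic/one-stage ratio has mean −ln b and SD √2·s, so before any selection

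P(ratio < 0.6) = Φ[(ln 0.6 + ln b) / (√2·s)], with ln 0.6 = −0.511.

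- FVIII (b = 1), s = 0.15: Φ(−0.511/0.212) = Φ(−2.408) = 0.8%.
- FVIII (b = 1), s = 0.25: Φ(−0.511/0.354) = Φ(−1.445) = 7.4%.

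The FIX bias does not appear in these two lines. A simulation with 400,000 draws per scenario, with true FIX assumed log-uniform on 0.003–0.40 IU/ml, gives the following among patients whose one-stage FIX is mild or moderate:

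| FIX bias b | SD s | FIX ratio < 0.6 | FVIII ratio < 0.6 |
|---|---|---|---|
| 1.0 | 0.15 | 0.8% | 0.8% |
| 1.0 | 0.25 | 8.1% | 7.5% |
| 1.3 | 0.15 | 12.5% | 0.8% |
| 1.3 | 0.25 | 25.6% | 7.5% |
| 1.67 | 0.15 | 51.3% | 0.8% |
| 1.67 | 0.25 | 51.9% | 7.4% |

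The FIX column responds to the bias; the FVIII column reflects assay noise alone.

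**3. Effect of leaving out severe patients, with FIX substituted.** The answer depends on which assay sets the label.

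*Label is the same one-stage result.* Nobody included has one-stage FIX below 0.01.

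- For the target class severe, true positives = 0 and false positives = 0. Sensitivity = 0/k, where k is the number of included patients who are severe by the chromogenic assay; specificity = 1. Both follow from the selection. With all haemophilia B patients included, simulated sensitivity is 0.57–0.93.
- A patient labelled too mild has a one-stage class milder than the chromogenic class, so at least moderate by one-stage. All such patients stay in (100%, by logic and in every scenario).
- Of patients labelled too severe, those at one-stage severe/chromogenic moderate drop out. About 45–50% of these errors remain in the simulation.

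*Label is the chromogenic result.* No included patient is chromogenic severe, so sensitivity for severe has a zero denominator, and about half of the labelled-too-mild errors are lost (50% remain).

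*Either way,* moderate versus mild at 0.05 IU/ml can be estimated among the patients included.

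**The case against.** The strongest reply is that this is a drafting slip with no doubt about intent. The heading, both objectives, section 2.4.3 and section 1.4.3 all point to FIX. FIX activity by both assays is among the laboratory tests in section 5.1.2, and baseline values by both are extracted under section 5.1.3. That stands, and it makes the remedy cheap. It does not remove the error: the lines at fault are the operative determinant and endpoint definitions.

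The mild and moderate restriction also has a defence. It appears consistently in sections 2.4.3 and 6.4.3, and section 1.4.3 can be read as saying who is assayed rather than who enters each analysis. Nor does the restriction hide the error that section 1.4.3 fears, patients labelled too mild, if the label is one-stage. This stands too; what remains is a difference in scope to be reconciled and a conditional limit on the accuracy estimates.

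A reader might infer several stronger points that the documents do not support:

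- **F8 has replaced F9.** It has not; F9 is still listed.
- **Sensitivity is 0 and specificity 100% as planned.** This needs the inclusion label to be the very one-stage result under evaluation, and a 0.01 cut-off. The protocol states neither. Section 4.1 relies on how patients are registered, section 1.4.3 says only that one-stage is the usual assay, and the case report form records one-stage, chromogenic and two-stage baselines.
- **The FVIII definition would yield almost no events.** That depends on assay precision; the assumed scenarios give 0.8% to 7.5%.
- **The ratio should count discrepancies in both directions.** A chromogenic/one-stage ratio below 0.6 matches the undertreatment concern in section 1.4.3, so the one-sided choice is not an error.

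**Conclusion.** The point holds for the factor. In section 6.4.3 the objective 1 determinant and endpoint and the objective 2 ratio are written on FVIII, against the FIX objectives of the same section, and F8 is an unneeded determinant beside F9. Read literally, neither primary objective can be answered, whatever the size of the FIX bias. This conclusion comes from the text alone; the percentages only illustrate it and rest on assumed bias, precision and FIX distribution.

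The population point holds in a conditional form. If the severity label is the one-stage result being evaluated, leaving out severe patients truncates errors across 0.01 IU/ml and fixes sensitivity and specificity for severe disease by selection. Misclassification is still measurable: patients labelled too mild remain visible, and the 0.05 IU/ml boundary can be estimated. It would be going too far to say that the exclusion of severe patients defeats the substudy.

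**What to change.** 1. In section 6.4.3, replace FVIII by FIX in the objective 1 determinant and endpoint, and define the large discrepancy as FIX:C chromogenic / FIX:C one-stage below 0.6.
2. Use F9 genotype only, in both the determinant and the analysis line of objective 2.
3. Reconcile the population in sections 2.4.3 and 6.4.3 with section 1.4.3, and name the assay that sets the severity class. Either analyse all haemophilia B patients with both FIX assays, giving sensitivity and specificity at 0.01 and 0.05 IU/ml, or keep mild and moderate patients and limit sensitivity and specificity to the 0.05 boundary, reported as moderate versus mild among those included.

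The cost is a protocol text amendment. No new assay is needed, since both FIX assays are already planned and baseline values are extracted from records. Because blood sampling is voluntary (section 5.1.2), the number with both results should be reported.

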2.4 General objective: To elucidate the variability in clinical phenotype among PWH

2.4.1 To assess the usefulness of The Calibrated Automated Thrombogram (CAT) assay in relation to clinical phenotype:

Main objectives:

1. To establish specific sample conditions to generate reliable CAT assay outcome parameters in patients with haemophilia.

Secondary objectives:

- To assess the association between the results of the CAT assay and the self-reported clinical bleeding phenotype of patients with severe, moderate and mild haemophilia.
- 2. To evaluate if the CAT assay can accurately diagnose the self-reported clinical bleeding phenotype of patients with severe, moderate and mild haemophilia.

2.4.2 To assess the usefulness of the Nijmegen Haemostasis Assay (NHA) in relation to clinical phenotype:

Main objectives:

- To assess the association between the results of the NHA and the self-reported clinical bleeding phenotype of patients with severe, moderate and mild haemophilia A and B.
- To evaluate if the NHA can accurately diagnose the self-reported clinical bleeding phenotype of patients with severe, moderate and mild haemophilia.

2.4.3 To assess misclassification of disease severity by the one-stage clotting assay in haemophilia B patients:

Main objectives:

 To assess the extent of discrepancy in FIX activity level as measured by the one stage clotting assay to the chromogenic assay in patients with mild and moderate haemophilia B. 2. To evaluate the association between F9 genotype and discrepancy between the FIX activity levels as measured by the one-stage clotting assay and the chromogenic assay in patients with mild and moderate haemophilia B.

2.4.4 To describe bleeding scores in children with haemophilia with the newly developed paediatric bleeding assessment tool (iCHEC):

Main objective:

- 1. To describe bleeding scores in all children with haemophilia
- 2. To describe bleeding scores according to haemophilia severity, age and treatment regimen (prophylaxis/on demand).

2.5 General objective: To assess immunological mechanisms that may lead to inhibitor formation in patients with haemophilia A

2.5.1 Specific objectives assessing the relationship between FVIII-specific non-neutralizing antibodies and inhibitor formation:

Primary objectives:

- 1. To assess the prevalence of FVIII-specific non-neutralizing antibodies (NNAs) among noninhibitor patients with severe, moderate and mild haemophilia A in the Netherlands.

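### Section 6.4.3, objective 2 asks about assay discrepancy in either direction, but its only endpoint counts low chromogenic-to-one-stage ratios, so a genotype that raises the ratio is poorly detected and misread

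*Protocol*

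**What the plan says.** Sections 2.4.3 and 6.4.3 state the objective in the same undirected terms: "To evaluate the association between F9 genotype and discrepancy between the FIX activity levels as measured by the one-stage clotting assay and the chromogenic assay". The analysis population is given as "The population will consist of all persons with mild and moderate haemophilia B", without a number.

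The endpoint in section 6.4.3 is binary and one-sided: "A large discrepancy between the result of the one-stage clotting assay and the chromogenic assay is defined as having a ratio of" chromogenic to one-stage activity "lower than 0.6". The analysis matches it: the association of genotype with "a discrepancy between the results of the one-stage clotting assay and the chromogenic assay will be assessed using logistic regression". There is no upper limit, no analysis of the ratio itself by genotype, and no reason for 0.6 at that place.

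Objective 1 of the same section describes the extent of discrepancy and gives sensitivity and specificity of the one-stage assay, but not by genotype.

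Section 1.4.3 gives the background. In mild and moderate haemophilia A the one-stage result was the higher one, and a patient labelled too mild might be undertreated. For haemophilia B it mentions one conference paper that found a discrepancy, with no direction given, and justifies the substudy as follows: "Given the scarcity of evidence for this phenomenon in the haemophilia B population".

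The section writes the ratio with FVIII symbols although the objective concerns FIX. That is a separate matter; the ratio is read here as a FIX ratio.

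**The concern.** Both assays return a continuous activity, so every patient has a continuous ratio. The endpoint keeps one bit of it and looks in one direction only. Two things follow.

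First, question and endpoint do not match. A genotype with chromogenic results well above one-stage results is a discrepancy under the objective, yet it is coded as its absence. At best, such a genotype would show an odds ratio below 1 and be reported as protecting against discrepancy.

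Second, where genotype moves the whole distribution of the ratio, the cut discards information. The subgroup is only part of the roughly 1260 participants expected, restricted to haemophilia B without severe cases and then divided by genotype. If ratios below 0.6 are uncommon, some cells will be sparse or empty and ordinary logistic estimates unstable.

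**Working it through.** **The plan's own figure.** Section 4.4: 1800 × 0.70 = 1260 participants, which reproduces. It covers all haemophilia types and severities. No number of patients, effect size, frequency below 0.6 or power is stated for section 6.4.3, so every power figure below rests on assumptions.

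**What the coding does.** Section 4.1 defines moderate disease as 0.01 to 0.05 IU/ml and mild as above 0.05 to 0.40. Two illustrative patients:

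| One-stage | Chromogenic | Ratio | Class by one-stage → chromogenic | Coded as large discrepancy |
|---|---|---|---|---|
| 0.08 | 0.04 | 0.5 | mild → moderate | yes |
| 0.04 | 0.08 | 2.0 | moderate → mild | no |

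Both differ by a factor of two and both change severity class. Only the first counts.

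**Power, shift in the expected direction.** Assume a normal log ratio with SD 1, two genotype groups of sizes n1 and n2 with N = n1 + n2, a shift of d SD in one group, a proportion p0 of the reference group below the cut, and two-sided alpha 0.05.

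- Continuous: power = Φ(d·√(n1·n2/N) − 1.96).
- Cut: p1 = Φ(z(p0) + d); power = Φ((|p1 − p0| − 1.96·SE0)/SE1), where SE0 is the pooled and SE1 the unpooled standard error.

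For N = 100 split 1:1, p0 = 0.10, d = 0.5:

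- Continuous: 0.5 × √25 = 2.5; 2.5 − 1.96 = 0.54; power 71%.
- Cut: p1 = Φ(−1.282 + 0.5) = 0.217; difference 0.117; SE0 = 0.0731, SE1 = 0.0721; (0.117 − 0.143)/0.0721 = −0.36; power 36%.
- Loss: 35 points.

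Simulation of the same comparison (t-test on the log ratio against the likelihood-ratio test for the cut):

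| N | Share in genotype group | Shift (SD) | Reference below cut | Log ratio | Cut |
|---|---|---|---|---|---|
| 100 | 20% | 0.7 | 15% | 80% | 55% |
| 100 | 40% | 0.5 | 15% | 69% | 45% |
| 150 | 20% | 0.7 | 5% | 92% | 53% |
| 60 | 40% | 0.7 | 30% | 74% | 56% |

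Over N = 60, 100, 150, shares of 20% and 40%, shifts of 0.5 and 0.7 SD, and 5%, 15% and 30% below the cut (36 settings), the loss is about 7 to 50 points.

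On a wider grid (N 60 to 200, share 20% to 50%, shift 0.3 to 1.0 SD, 5% to 50% below the cut) the formulas give 0 to 49 points, and 13 to 49 where the continuous test has 50% to 95% power. Losses near zero occur where both tests have very high power; small losses also occur where both have very low power.

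**Power, shift in the opposite direction.** N = 100, p0 = 0.10, d = 0.8, so p1 = Φ(−1.282 − 0.8) = 0.019.

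- Split 1:1. Continuous: 0.8 × 5 − 1.96 = 2.04, power 98%. Cut: difference 0.081, SE0 = 0.0473, SE1 = 0.0465, (0.081 − 0.093)/0.0465 ≈ −0.24, power 40%.
- 20% in the genotype group: 89% against 11%. The expected count below the cut in that group is 20 × 0.019 ≈ 0.4, so the approximation is rough.

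With the shift reversed in the four simulated settings above, the cut had 10% to 44% power.

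**A setting where the cut does better.** Suppose only some variants in a genotype group are discrepant: N = 100, 40% in the group, 20% of those shifted by 3 SD, 2% of the reference group below the cut. Simulated power is 62% for the log ratio and 84% for the cut.

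**The case against.** The low-side cut has a stated purpose. The section is about one-stage results that make disease look milder than it is, and section 1.4.3 names undertreatment as the harm. That harm arises only when the one-stage result is the higher one, which is what a low ratio captures. A prespecified threshold with a matching logistic model is a legitimate answer to the question of which genotypes give a large discrepancy of that kind. Section 1.4.3 also says that certain mutations drive the discrepancy in haemophilia A, which fits the mixed-group setting where the cut has more power.

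All of this stands as a reason to keep the below-0.6 result. It does not make that result sufficient: the objective is worded without direction, the direction is taken from another disease, and no other planned analysis shows the ratio by genotype. A statistical analysis plan may add analyses, but the protocol itself fixes this endpoint, cut and model.

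Three stronger readings are tempting and are not supported:

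- A reader might take 7 to 50 points as the power this plan loses. It describes the assumed grid; none of its inputs is in the protocol.
- A reader might infer that a genotype effect in the opposite direction cannot be found at all. Power there is reduced, often severely, but is not zero.
- A reader might call 0.6 arbitrary because no source is cited beside it. Whether it is an established threshold cannot be judged from the protocol.

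**Conclusion.** The mismatch is certain from the text: an undirected objective has a one-sided binary endpoint as its only measure, and high ratios are counted with the concordant patients. A genotype effect in that direction would be detected poorly and reported as less discrepancy.

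The loss of power is conditional. It is about 7 to 50 points for a uniform shift under the assumed sizes, near zero in some other settings, and reversed if only a few variants in a group are strongly discrepant. Since the protocol does not say which case applies, the sound conclusion is that the cut should not stand alone, not that it should be removed. The change is worth making: as written, the substudy answers only half of its own question.

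**What to change.** In section 6.4.3, objective 2:

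1. Analyse the log of the chromogenic-to-one-stage FIX ratio by linear regression on F9 genotype group, and report the geometric mean ratio with 95% CI per genotype.
2. Keep the logistic analysis of ratios below 0.6 beside it, labelled as the result tied to under-classification of severity.
3. Report by genotype the proportion with a ratio above 1/0.6 (about 1.67), the mirror of 0.6 on the log scale.

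The cost is a few sentences and one more analysis. The same two assay results are used, with no extra patients or blood. Values below an assay's detection limit will need a censored or sensitivity analysis.
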